The closest estimation to our magnitude of NST was found by Claessens-can Ooijen et al., which a 17% increase in EE was detected in lean male subjects.¹⁷ It is worth noting that the testing conditions were quite different in this study, where all measurements were conducted at 15°C. The thermoneutral state was defined when the subjects wore standard clothing consisted of sweat shirts and pants (clo =0.71) and covered with a duvet (clo=6.8). When the duvet was removed, the 1-hr exposure was defined as mild-cold. It is possible that a steady-state EE was not achieved by this design. Davis¹⁸ reported a 34% increase over resting following 31 days of exposure to 12 °C for 8 h per day where significant shivering at the first 20+days. While this is believed to be an acclimation effect but demonstrates a very significant potential capacity in healthy lean men. It was not understood at that time that brown fat was heat-producing.

In summary, the preliminary results from 12-DK-0097 demonstrate that 1) a suitable experimental system can be devised to measure the capacity for NST in humans and 2) the NST contribution to EE is greater than previously recognized.

The two major questions asked in this protocol are:

- ***What are the mechanisms driving human NST?***
- ***What are the effects of drugs on human BMR?***

I.1 Scientific and Clinical Significance

The high prevalence of obesity is a major public health concern. Small differences in energy expenditure, if not compensated by changes in food intake, would have long-term effects on body weight.^{19,20} Mild cold environmental temperatures elevate energy expenditure in humans, likely via BAT activation⁴. It is plausible that an increasingly thermoneutral environment is contributing to the obesity epidemic. Conversely,

increasing heat production via lowering of environmental temperature could be a potential approach to combat obesity. This study will expand our understanding of the mechanisms underlying human thermal physiology in a temperature range that is close to those encountered in daily indoor living. Moreover, several FDA-approved drugs' (such as anti-obesity drugs) currently on the market may act through mechanism(s) that modulate BMR and/or NST, however, no previous studies have rigorously quantified their impact with precise measurements as we plan to accomplish in this protocol.

I.2 Mechanistic basis for NST

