Cohort 1 is a single-blind, fixed order (for drug treatment), partially randomized (for temperature), cross-over study, with data analysis performed in a blinded manner

All study volunteers will undergo the screening visit evaluation as outlined in Table 2, including a medical and laboratory examination to determine study eligibility. Qualifying volunteers will be invited for the full study at the Metabolic Clinical Research Unit as inpatients. An initial one-day equilibration diet will be standard before metabolic testing. This equilibration period will also serve as an orientation/ acclimatization to the metabolic chamber and procedures.

Table 2. Screening tests:

Eligibility phone contact pre-screen questionnaire	
1st REG H+P or Protocol Screen Progress note	
Temp, Pulse, BP, RR, WT, HT	
Nutritional consult	
Informed Consent Version:	
Consent documented in CRIS	
Eligibility Criteria Documentation	
Clinical Labs/Procedures	
EKG	
CBC with Differential	
Acute care + hepatic + mineral panels (Chem 20)	
Lipid Panel	
Thyroid (TSH)	
Toxicology (urine)	
Ferritin	

To match the criteria from 12-DK-0097, we will recruit subjects who do not work in a cold environment and are not trained athletes. Drugs will be administered exactly at 8:00 am (+/- 15 minutes), (except dantrolene, which will be administered at 6:00 am (+/- 15 minutes), and bolus magnesium sulfate (~ 30 min infusion) at 7:30 AM (+/- 30 minutes) and maintenance infusion at 8:00 AM (+/- 15 minutes)), upon entering the metabolic chamber. We will measure REE at times close to the Tmax of the drugs (9:30-10:00 and 10:30-11:00).

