During a 17-day admission (with 4 off days on pass) to the NIH Hatfield Clinical Research Center, study volunteers will undergo daily EE measurements (up to 4 hours) in a metabolic chamber with temperatures set between 18.0 to 21.0 and 27.0°C. Individualized determination of the lowest environmental temperature that does not cause shivering is important to maximize assay sensitivity. This will be accomplished by using the mini-adaptive design approach (Table 3): On Day 2, the first full inpatient study day, volunteers will be acclimatized to the metabolic chamber at 19.0°C, wear multiple body sensors, and undergo standard testing procedures that will be repeated throughout the study. If shivering occurs on Day 2 at 19.0°C, the chamber temperature will be set to 20.0°C on Day 3. If shivering occurs at 20.0°C on Day 3 the low temperature will be

21.0°C; if no shivering at 20.0°C on Day 3, the low temperature will be 20.0°C. If no shivering occurs on Day 2, then the chamber temperature will be set to 18.0°C on Day 3. If shivering occurs at 18.0°C on Day 3 the low temperature will be 19.0°C; if no shivering at 18.0°C on Day 3 the low temperature will be 18.0°C.

Table 3

Day 2 chamber temperature	Day 2 result	Day 3 chamber temperature	Day 3 result	Low Temperature
19C	Day 2 shiver	20C	Day 3 shiver	21C
			Day 3 no shiver	20C
	Day 2 no shiver	18C	Day 3 shiver	19C
			Day 3 no shiver	18C

Table 4 Protocol flow

day	1	2	3	4	5	6	7	8	9	10	11	12	13	14	15	16	17
	Sat	Sun	Mon	Tue	Wed	Thu	Fri	Sat	Sun	Mon	Tue	Wed	Thu	Fri	Sat	Sun	Mon
drug		pbo	pbo	pbo	pbo	pro	pro	off	off	dan	dan	Mg	Mg	pin	off	off	pin
temp.		19	18 or 20	low	27	low	27			low	27	27	low	27			low
notes	admit							pass		return					pass		return
blood				X,X	X,X	X	X			X	X	X	X	X			X

Where *pbo*=placebo, *pro*=propranolol (oral 160mg PD), *dan*=dantrolene (oral 100mg PD), *Mg*=magnesium sulfate (IV), and *pin*=pindolol (oral 20mg PD).

On Days 4-17, chamber temperature will be varied as indicated in Table 4 and procedures will be repeated. Temperatures will be block randomized (one day at the low temperature and one at 27.0°C), with blocks being: Days 4,5; Days 6,7; Days 10,11; Days 12,13; and Days 14,17. Subjects will not be informed of the environmental temperature.

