Oral medications are placebo on Days 2, 3, 4, and 5; regular propranolol (not sustained release) 160 mg on Days 6 and 7; dantrolene 100 mg on days 10 and 11, pindolol 20 mg on Days 14 and 17; and magnesium sulfate on Days 12 and 13. Since it is not possible for all medications to have the same appearance, drug or placebo will be administered by Clinical Center personnel without subjects being able to see or taste the medication. The off-days (weekends) serve as washouts for propranolol and pindolol. Since both dantrolene and magnesium sulfate function as muscle NST inhibitors, minimum washout is needed. Finally, magnesium sulfate has a half-life of ~4 hrs, thus its impact on EE of the next day is minimum. This compact schedule is the result of balancing the rigorous study design and the feasibility for the subjects.

For each chamber study, volunteers will be fasted after midnight and during the up to 4-hour study period while they are in the chamber. During this time, all subjects will be asked to minimize their physical activity while staying awake in a reclining position in the designated chair in the chamber. Between 9:30-10:00 and 10:30-11:00 AM, the subject is required to lower the ambient lighting and recline without any physical activity, but remain awake. Clothing will be standardized and limited to the following: one pair of undershorts, one sleeveless form-fitting cotton shirt, one pair of

form-fitting shorts, and one pair of light socks (issued by the inpatient unit), for a combined thermal insulation value of 0.36 (clo).⁹⁴ After each chamber study, participants will return to the inpatient room on the 5SW inpatient unit at a comfortable range between 23-25°C for the remainder of the day until the next morning. All meals will be served in the patient rooms. Each afternoon, study volunteers will have a standard walking session from 15:00-15:30 on a treadmill. The pace of the walking will be self-selected but will be standard throughout the inpatient study period for each individual and reflect the subject's prior activity level.

Subjects will be allowed to go on pass on Cohort 1 Days 8/9, 15/16, but refrain from increased exercise, exposures to extreme temperatures, and all caffeine intake, and must return before dinner. If deemed necessary, at the discretion of the Principal Investigator, any of the pass durations may be increased.

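### Cohort 1 gives placebo first and the drugs in one fixed order, so each drug-minus-placebo difference at the low temperature is confounded with cold-exposure number, and the plan neither checks nor acknowledges this

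*Combined protocol and SAP*

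**What the plan says.** Section III.2-1 describes the design: "Cohort 1 is a single-blind, fixed order (for drug treatment), partially randomized (for temperature), cross-over study". The schedule in the same section is "Oral medications are placebo on Days 2, 3, 4, and 5; regular propranolol (not sustained release) 160 mg on Days 6 and 7", followed by "dantrolene 100 mg on days 10 and 11, pindolol 20 mg on Days 14 and 17; and magnesium sulfate on Days 12 and 13". No placebo session comes after Day 5. Randomisation is confined to temperature order within each pair of days: "Temperatures will be block randomized (one day at the low temperature and one at 27.0°C".

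Days 2 and 3 are placebo sessions in the cold that choose each participant's low temperature (Table 3). For example, "if no shivering at 18.0°C on Day 3 the low temperature will be 18.0°C", and on the other arm of the rule, "if no shivering at 20.0°C on Day 3, the low temperature will be 20.0°C". Energy expenditure (EE) heads the list of measurements made at every chamber stay. Section III.9 pays for 12 stays, which matches Days 2–7, 10–14 and 17 (6 + 5 + 1), so Days 2 and 3 are on file.

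Section II.1 predicts that propranolol, dantrolene and magnesium will each lower resting EE at the low temperature (REE_Low) by at least 5%. For propranolol and dantrolene it adds a comparison of the number who shiver with the number on placebo. The pindolol hypothesis concerns the difference between 27°C and low temperature on pindolol. Section II.2 adds a comparison of each drug's difference with the placebo difference. The schedule is defended on washout and feasibility. Period effects are not mentioned, and no period analysis is planned.

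**The concern.** In a crossover study with one fixed sequence, treatment and period are the same variable. Anything that changes with repeated cold or chamber exposure, or with time in hospital, enters the drug-minus-placebo difference in full. A declining response to cold would look like the hypothesised reductions for propranolol, dantrolene and magnesium. A rising response would hide them. The shivering comparison has the same weakness.

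The protocol treats exposure effects as real elsewhere. It gives Day 2 over to getting used to the chamber, cites a study of repeated cold exposure in which EE rose ("While this is believed to be an acclimation effect but demonstrates a very significant potential capacity in healthy lean men"), and randomises treatment in Cohorts 2 and 3. What is at stake is the mechanistic claim: whether a lower REE_Low can be put down to receptor or muscle blockade.

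**Working it through.** **1. Position of each low-temperature session.** Cold exposures fall on Day 2, Day 3, and then once in each block, whichever order the temperature randomisation gives.

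| Block | Days | Cold exposure no. | Largest gap from placebo low session |
|---|---|---|---|
| Placebo | 4, 5 | 3 | – |
| Propranolol | 6, 7 | 4 | 7 − 4 = 3 days |
| Dantrolene | 10, 11 | 5 | 11 − 4 = 7 days |
| Magnesium | 12, 13 | 6 | 13 − 4 = 9 days |
| Pindolol | 14, 17 | 7 | not the primary contrast |

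The numbers are the same for every participant, so the aliasing is complete.

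**2. Repeated placebo sessions (Table 3).** Low temperature 18 or 20°C: Day 3 repeated on Day 4/5, one exposure apart. Low temperature 19°C: Day 2 repeated on Day 4/5, two exposures apart. Low temperature 21°C: no repeat. There is no repeat at 27°C.

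**3. The plan's power (Section III.1).** Inputs: 12 completers, true difference 5%, stated power 0.98 at alpha 0.05 and 0.94 at 0.05/4. Two-sided paired t-test, noncentral t, 11 df:

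- SD 3.7% (the spread quoted for maximum NST): 0.989 and 0.932, close to the stated values.
- SD 2.54% (the within-subject figure, from BMR in the thermoneutral zone): 1.000 and 0.999, so 0.94 is not reproduced.

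Both SDs are carried forward. The plan's power assumes that no period effect enters the difference.

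**4. False positives under an assumed drift.** Let d be the total shift in REE_Low between the placebo and drug sessions, with no drug effect. SE = SD/√12, which is 0.733% or 1.068%. The critical mean is t(0.975, 11) × SE = 2.201 × 0.733 = 1.61%, or 2.201 × 1.068 = 2.35%. The rejection probability uses the noncentral t with noncentrality d/SE.

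| Assumed d | SD 2.54% | SD 3.7% |
|---|---|---|
| 0.5% | 0.10 | 0.07 |
| 1.0% | 0.24 | 0.14 |
| 1.5% | 0.46 | 0.25 |
| 2.0% | 0.70 | 0.40 |

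In the other direction, a 2% upward drift against a true 5% fall leaves 3% to detect. Power at alpha 0.05 is then 0.96 (SD 2.54%) or 0.73 (SD 3.7%).

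**5. Precision of the placebo repeat.** The 95% half-width with 12 pairs is 1.61% (SD 2.54%) or 2.35% (SD 3.7%). With 9 pairs it is 1.95% or 2.84%.

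**6. Cost of extrapolating that drift.** If the repeats are one exposure apart and the drift is projected k exposures forward, the adjusted contrast is D − (1+k)·P(4/5) + k·P(3). With equal independent session errors, its SD is the paired SD times √[(1 + (1+k)² + k²)/2], a factor of 1.73, 2.65 and 3.61 for k = 1, 2, 3 (propranolol, dantrolene, magnesium). Power for a true 5% effect at alpha 0.05 becomes 0.95/0.65/0.41 (SD 2.54%) or 0.69/0.37/0.22 (SD 3.7%).

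**The case against.** The strongest reply is that nothing in the documents shows drift occurring. The acclimation study they cite used 31 days at 12°C for 8 hours a day, with shivering, against seven sessions of up to 4 hours at 18–21°C here. EE rose in that study, which would work against the three predicted reductions. Two cold placebo sessions precede the reference, and diet, clothing, activity and behaviour on pass are controlled. The assumed drifts are smaller than the 5% target. The order is openly labelled as fixed. All of this stands. It makes large drift less likely but does not measure it, and no design feature separates drift from drug.

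A reader might infer that pindolol, last in the order, is the most exposed. The documents do not support that for its primary contrast. Temperature order is randomised over Days 14 and 17, so drift common to both temperatures cancels. Cold-specific habituation does not cancel, and it would shrink the difference towards the predicted result. The secondary comparison with the placebo difference remains confounded.

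A reader might also infer that drift should be extrapolated by exposure number and subtracted, with an effect accepted only if it survives both analyses. Step 6 of the working shows that this could often reject a genuine 5% effect. Nothing in the documents supports linearity, particularly across weekends on pass, and in the 19°C branch the first session is the Day 2 acclimatisation session.

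**Conclusion.** The point holds as a limit on attribution. For propranolol, dantrolene and magnesium, the REE_Low difference from placebo is fully aliased with cold-exposure number, at most 9 days apart. The shivering comparison is aliased in the same way. For pindolol, only cold-specific drift touches the primary contrast.

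It would go too far to conclude that the Cohort 1 results are biased. The false-positive probabilities (0.10 to 0.70 at SD 2.54%, 0.07 to 0.40 at SD 3.7%) rest on assumed drifts of 0.5 to 2.0%, 12 completers, a two-sided paired t-test at 0.05 and no drug effect. They show how small a drift would matter, not how large it was. The recorded placebo repeats can flag early drift but cannot clear the later drugs.

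**What to change.** Cohort 1 enrolment is complete, so the changes concern analysis and wording.

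1. Report descriptively, with a 95% confidence interval, the within-participant change in placebo REE from the matching Day 2 or Day 3 session to the Day 4/5 low-temperature session, for participants whose low temperature is 18, 19 or 20°C. Show the 19°C branch separately.
2. Show each drug effect unadjusted, beside a sensitivity display over a stated range of assumed drift. Use no linear extrapolation and no rule requiring significance in both analyses.
3. State in the Cohort 1 objectives and conclusions that drug is confounded with period, so a difference from placebo cannot be attributed to the drug alone unless it exceeds plausible drift.

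The cost is some analysis-plan wording and one extra analysis of recorded data. The check has limits that should be stated with it. It covers Days 2 to 5 only, uses sessions selected for absence of shivering, has no repeat at 21 or 27°C, and is imprecise (half-width about 1.6 to 2.35% even with 12 pairs). It is post hoc if the data are already unblinded, which the documents do not say. The mechanistic claims become somewhat weaker.

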If the predominant signaling to human NST mechanisms is via β -adrenergic receptors, one expects that by clamping β -adrenergic tone with pindolol, the same level of change in REE_{Low} and REE_{27°C} will be observed. Since pindolol is a partial agonist, the prediction is that this clamped EE will be elevated moderately at a level between REE_{27°C} and REE_{Low} with placebo.

Dantrolene

To differentiate NST from skeletal muscles, we will use the following two pharmacologic agents. Dantrolene (Dantrium, label:

http://www.accessdata.fda.gov/drugsatfda_docs/label/2012/017443s043s046s048s049lbl.pdf) is clinically indicated for treatment of muscle spasticity⁴² and of malignant hyperthermia⁴³. Dantrolene binds and inhibits the muscle ryanodine receptor (RyR1), which releases calcium from the sarcoplasmic reticulum^{44,45}. A recent study in mice suggests that dantrolene blocks muscle NST, but has no effect on BAT NST²⁴.

Clinical dosing of dantrolene for spasticity is via titration from 25 mg QD to up to 100 mg TID, or even 100 mg QID (label). The pharmacokinetics of a single 100 mg oral dose of dantrolene include a Cmax at ~4.5 hours of 0.7-1.45 ug/ml (2.2-4.6 uM; Mr is 314), and t_{1/2} of 9-12 hours⁴⁶⁻⁴⁸. Single oral doses as high as 150 mg have been reported⁴⁷.

It is not clear what level of dantrolene is needed to maximally inhibit RyR1. Dantrolene is hydrophobic and highly bound to albumin⁴⁹, but we are not aware of any clinical measures of free drug levels. Thus, how an in vitro IC50 of 300 nM⁴⁵ corresponds to the exposure achieved with a single 100 mg oral dose of dantrolene is unknown.

We are not aware of prior studies of the effect of dantrolene on EE under conditions similar to those in this protocol. The prediction is that a single oral 100 mg oral dose of dantrolene will significantly inhibit muscle NST in humans.

Magnesium sulfate

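### The reason given for minimal washout between dantrolene and magnesium does not protect the magnesium comparison: REE_Low is open to possible, unquantified dantrolene carryover when the low-temperature session falls on Day 12

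*Combined protocol and SAP*

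**What the plan says.** Section III.2-1 (Protocol design, Cohort 1) fixes the drug order and sets the days: "dantrolene 100 mg on days 10 and 11, pindolol 20 mg on Days 14 and 17; and magnesium sulfate on Days 12 and 13". The weekends serve as washout for propranolol and pindolol. For the step from dantrolene to magnesium the reason given is "Since both dantrolene and magnesium sulfate function as muscle NST inhibitors, minimum washout is needed". The next sentence argues from magnesium's half-life of about 4 hours that little of it reaches the following day.

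Section I.2 (Dantrolene) states: "The pharmacokinetics of a single 100 mg oral dose of dantrolene include a Cmax at ~4.5 hours of 0.7-1.45 ug/ml", with a "t_{1/2} of 9-12 hours". It also says that the level needed for maximal RyR1 inhibition is not clear. Section I.2 names RyR1 as a target of both dantrolene and magnesium.

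Section II.1 tests each drug separately for a fall in REE_Low of at least 5%. The magnesium hypothesis omits the word placebo that the dantrolene hypothesis contains; I read the comparator as placebo.

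Temperature order is randomised within two-day blocks, "with blocks being: Days 4,5; Days 6,7; Days 10,11; Days 12,13; and Days 14,17". Table 4 as printed shows 27°C on Day 12 and the low temperature on Day 13. No allocation ratio is given.

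**The concern.** If the earlier drug acts on the same target, in the same direction and on the same endpoint, whatever is left of it adds to the apparent effect of the later drug. A shared mechanism is thus a reason to look harder at carryover. The half-life argument covers only what follows magnesium, not what precedes it.

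Because magnesium follows dantrolene in every participant, the design cannot average a carryover effect out. At stake is Objective 4: part of any fall in REE_Low credited to magnesium could come from dantrolene. Participants with the low session on Day 13 have the 27°C session on Day 12, so for them the question moves mainly to the secondary difference between temperatures.

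**Working it through.** **The plan's own figure.** The documents give no residual dantrolene fraction. The only design figure that covers the magnesium comparison is the power in Section III.1: 12 completers, 5% difference, 0.98 at alpha 0.05 and 0.94 at 0.05/4. A two-sided paired t-test gives 0.992 and 0.946 with SD 3.59% (2.54 × √2), and 0.989 and 0.932 with SD 3.7%. With 2.54% as the SD of the difference it gives over 0.999 and 0.999. The stated figures fit an SD of about 3.6-3.9, so I carry both 2.54 and 3.59 (or 3.7) below.

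**Timing inputs.** Dantrolene is given at 06:00 and peaks at about 4.5 h (10:30); its half-life is 9-12 h (Section I.2). REE is measured at 09:30-10:00 and 10:30-11:00 (Section III.2-1). The windows therefore run from 27.5 to 29 h after the last dose on Day 12 and from 51.5 to 53 h on Day 13.

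**Half-lives elapsed since the last dose.**
- Day 12: 27.5/12 = 2.3 to 29/9 = 3.2.
- Day 13: 51.5/12 = 4.3 to 53/9 = 5.9.
- The 4 days that Section I.3 calls adequate: phentermine 96/19 = 5.1; topiramate 96/21 = 4.6.

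**Residual fraction.** Last dose: 2^(−(t − 4.5)/t½). Day 10 dose: 2^(−(t + 24 − 4.5)/t½). Both are relative to a single-dose peak.

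| Session | t½ | Last dose only | Both doses |
|---|---|---|---|
| Day 12 | 9 h | 15.2-17.0% | 17.5-19.7% |
| Day 12 | 12 h | 24.3-26.5% | 30.4-33.1% |
| Day 13 | 9 h | 2.4-2.7% | 2.8-3.1% |
| Day 13 | 12 h | 6.1-6.6% | 7.6-8.3% |

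A one-compartment oral model fitted to the 4.5 h peak gives 18-29% (last dose) and 21-37% (both doses) on Day 12, and about 3-9% on Day 13.

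**What this could mean for the endpoint (illustration only).** Assume that effect is proportional to concentration, dantrolene truly lowers REE_Low by 5%, and magnesium does nothing.
- Low session on Day 12: 5 × 0.15 = 0.75 to 5 × 0.33 = 1.65 points of apparent magnesium effect.
- Low session on Day 13: 5 × 0.024 = 0.12 to 5 × 0.083 = 0.42 points.
- Half on each day: (0.75 + 0.12)/2 = 0.43 to (1.65 + 0.42)/2 = 1.03 points. With n = 12 and SD 2.54-3.7, the type I error at nominal 0.05 becomes 0.07-0.25.

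**What the data can show by order.** If allocation is 1:1, each order has about 6 participants. Power for a 5% effect:

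| n | SD | alpha 0.05 | alpha 0.05/4 |
|---|---|---|---|
| 6 | 2.54 | 0.97 | 0.78 |
| 6 | 3.59 | 0.78 | 0.46 |
| 12 | 2.54 | >0.999 | 0.999 |
| 12 | 3.59 | 0.99 | 0.95 |

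On the illustration, the two orders differ by 0.75 − 0.12 = 0.63 to 1.65 − 0.42 = 1.23 points. A comparison of 6 with 6 has power of about 0.06-0.12 to detect that (SD 2.54-3.7).

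**The case against.** The strongest reply is that a residual concentration is not a residual effect. The protocol says that the inhibitory level of dantrolene is unclear and that free drug levels have not been measured. This stands. A reader might infer from the decay figures that the magnesium result is contaminated; the documents support only that it may be. The same uncertainty means that the residual cannot be assumed harmless.

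Second, Objective 4 concerns REE_Low only, and Table 4 prints that session on Day 13, when 2-8% remains. This limits the point: the 15-33% figure does not apply to every magnesium measurement. It does not remove the point, because the text under Table 4 randomises the order. That about half of the participants have the low session on Day 12 is an assumption.

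Third, even on the proportional assumption the average spurious effect is 0.4-1.0 points, well short of the hypothesised 5%. That is fair against the 5% threshold, less so against the zero null used in the power calculation.

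Fourth, the schedule is openly described as a compromise with feasibility, and drugs are not compared with each other. Both are true, but Objective 4 is still specific to magnesium.

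Finally, one might want to rest the magnesium conclusion on Day 13 sessions alone. That goes too far: at 0.05/4 it cuts power from 0.95-0.999 to 0.46-0.78. It would also be a post hoc change after enrolment was complete, and Day 13 is always the second magnesium day.

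**Conclusion.** The washout rationale is wrong as written: a shared mechanism makes carryover harder to recognise, and the stated 9-12 h half-life is not addressed. The primary magnesium outcome is open to possible bias toward a larger reduction in participants whose low session falls on Day 12. There, 15-27% of peak remains from the last dose (18-33% of a single-dose peak with both doses), 2.3-3.2 half-lives after dosing. On Day 13 the residual is about 2-8%.

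These figures assume first-order decline from the stated peak time, and dosing and measurement on schedule. The size of the bias in REE_Low is not known; the 0.4-1.0 points for an even split rest on a proportional effect and a true 5% dantrolene effect, neither of which the documents establish. They do not support the reading that the magnesium effect has been shown to be contaminated.

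**What to change.** 1. Reconcile the washout rationale in Section III.2-1 with the dantrolene half-life in Section I.2, and Table 4 with the block-randomisation text. State the allocation ratio and how many participants had the low magnesium session on each day.
2. Keep the all-participant comparison of magnesium with placebo REE_Low as primary.
3. Add a sensitivity analysis, labelled as added after Cohort 1 enrolment was complete, that gives the within-participant difference from placebo REE_Low with its confidence interval separately for low on Day 12 and low on Day 13.
4. Word the conclusion as magnesium with possible residual dantrolene, unless the Day 13 estimate is consistent with it. Define consistent before the results by order are seen, and do not treat a non-significant difference between orders as evidence of no carryover.

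The cost is wording and one analysis of existing data; no treatment day changes. The limits are about 6 participants per order if allocation is 1:1, order confounded with first or second magnesium day, and little power to compare the two orders.
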